1.2 SCHEMA

1.3 SCHEDULE OF ACTIVITIES (SOA)

Procedures	Pre-Index Visit	Index Visit – first eligible visit with primary care	0 to 6 months after Index visit	6 to 12 months after index visit	12 to 18 months after index visit
Select study clinics	Х				
EHR data is exchanged with Wizard web service in the background at the patient's first and subsequent primary care encounters occurring during the study duration. An encounter-based limited data set is collected and stored in a data repository (intervention & control)	х	X	X	x	Х
All eligible patients are randomly assigned a study identification (ID) the first time they are eligible for CDS at a study clinic		х			
Based on the study ID, an eligible patient is then randomly assigned to adherence intervention or control		Х			
After Wizard determines study eligibility and CDS recommendations, it prompts CDS tools to be printed for the intervention-assigned patient and their provider through a Best Practice Advisory (BPA) for rooming staff at each primary care encounter during the study period		X	х	X	X
The eligible intervention-assigned patient has an attempted exposure to Adherence CDS at each primary care encounter during the study period		Х	Х	X	Х
Wizard algorithms are run outside of encounters on all study eligible patients at set intervals (6, 12, and 18 months) for analysis purposes. A limited data set is collected and stored in a data repository (intervention & control patients)			Х	X	X
An eligible intervention-assigned patient is added to a pharmacist outreach intervention registry if study criteria are still met (not at goal and not adherent)			x		
An eligible intervention-assigned patient is assigned to a pharmacist			Х		
Pharmacist calls eligible patient (multiple attempts) for adherence assessment and action plan				X	×
Pharmacist follow-up per action plan				X	Х
Experience and satisfaction surveys sent to a random group of patients (intervention & control)			Х	X	

Procedures	Pre-Index Visit	Index Visit – first eligible visit with primary care	0 to 6 months after Index visit	6 to 12 months after index visit	12 to 18 months after index visit
Safety monitoring per Data Safety Monitoring Board (DSMB) plan (intervention & control)	Х	Х	Х	Х	Х

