In the 2018 version of Epic (Epic Systems Corporation), a measure of adherence similar to a calculated PDC is made available at encounters based on the total number of days supplied for a specified measurement period of time (default time being 6 months) prior to a clinical encounter. According to Epic, 'Medication adherence is determined by comparing a patient's current outpatient medication list in Epic with the number of times a medication has been dispensed.'⁴¹ In Epic, PDC is expressed as the percent of days in the measurement period before the encounter covered by medication fills for a specific medication based on data from Surescripts, an information technology company that supports e-prescription with the most comprehensive prescription dispense data in the United Sates. An indicator of confidence in the e-PDC (high, medium, or low) is also determined and displayed with the e-PDC score based on a determination of how accurate or reliable the Surescripts data is. The confidence is high if a patient fills all their prescribed medications from a pharmacy that reports all their dispense data to Surescripts; medium if high criteria is not met but there is some dispense and claims data available; low if a patient fills their prescribed medications from different pharmacies, some of which do not report to Surescripts and no claims data is available⁴¹.

For this intervention, the Epic pre-calculated PDC score has the advantage of being available for most patients seen in the care system rather than being limited to a subset of patients with HealthPartners insurance claims data available, which would be the case if we were to calculate PDC ourselves in the traditional methods using claims data. Because of the clinical advantages of e-PDC over calculated PDC, the MAS has been chosen for this study as the objective measure of medication adherence for intervention and study outcomes.

The New Care Paradigm includes Pharmacists

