9 STATISTICAL CONSIDERATIONS

9.1 STATISTICAL HYPOTHESES

• Primary Efficacy Endpoint(s):

For patients 18 to 75 years old not at goal for BP, A1C, or statin use and with medication nonadherence, those randomly assigned to the ReachOut Adherence Intervention will have improved adherence and clinical outcomes compared to those randomly assigned to control.

Hypothesis 1.1 Relative to those assigned to control, eligible adults with uncontrolled BP and baseline nonadherence to one or more BP medications who are assigned to intervention will be more likely to achieve (a) an e-PDC \geq 80% for all BP medications and (b) a reduction in systolic BP in the 12-month period after the index visit.

Hypothesis 1.2 Relative to those assigned to control, eligible adults with diabetes and A1C \geq 8% and baseline nonadherence to a non-insulin glycemic medication who are assigned to intervention will be more likely to achieve (a) e-PDC \geq 80% for all non-insulin glycemic medications and (b) a reduction in A1C values in the 12-month period after the index visit.

Hypothesis 1.3 Relative to those assigned to control, eligible adults with inadequately managed lipid disorders with baseline non-adherence to a statin who are assigned to intervention will be more likely to achieve an e-PDC \geq 80% for a statin in the 12-month period after the index visit.

• Secondary Efficacy Endpoint(s):

Assess the cost and cost-effectiveness of the ReachOut Adherence Intervention from the health system (payer) perspective through empirical analysis and microsimulation modeling of patient utilization and disease outcomes.

Hypothesis 2.1: Relative to those who are assigned to control, eligible study subjects who are assigned to intervention will have significantly higher overall health care costs in the 12-month period following the index visit, after controlling for demographics and baseline clinical risk factors.

Hypothesis 2.2: Relative to those who are assigned to control, eligible study subjects who are assigned to intervention will have significantly lower overall resource use and fewer major CV and diabetes-related events in a 30-year post-intervention simulated analysis using cost-effectiveness microsimulation modeling methods.

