9.2 SAMPLE SIZE DETERMINATION

H1.1 (BP): Based on preliminary data collected in our study clinics between August 6, 2019 and December 23, 2019, we anticipate that 2,132 patients will meet study eligibility criteria of having at least one antihypertensive medication with e-PDC <80% over a 6-month enrollment period. For power analysis, we adjusted this estimate by half (N=1,066) to conservatively account for a potential continuation of the current decrease in office visit secondary to clinic, visit and provider changes as part of COVID-19 pandemic response. Further assuming a two-sided α =0.05, equal comparison groups (1:1 intervention/control), and a probability of outcome (adherence) in the control group of 50%, the analysis for H1.1a will have 80% power to detect a difference in the proportion of patients with 12month e-PDC ≥80% of 8.7% or more (e.g., 50.0% in control patients vs. 58.7% in intervention patients). For pre-post analyses of SBP outcomes, we estimate that to detect a clinically meaningful difference in mean 12-month SBP of 3 mmHg, assuming 80% power, α =0.05, SD=15.8, 1:1 intervention/control, and ρ =0.5 (correlation of repeated measures), a sample size of N=872 patients will be required. Given the projections described above (N=1,066), we expect sufficient enrollment to meet this target sample size.

H1.2 (Glycaemia): From preliminary data we estimate that 1,664 patients will meet study eligibility criteria due to having at least one non-insulin glucose medication with e-PDC <80% and having a most recent A1C \geq 8%. Adjusting this estimate by half (as above) we anticipate N=832. Assuming a two-sided α =0.05, equal comparison groups (1:1 intervention/control), and a probability of outcome (adherence) in the control group of 50%, the analysis for H1.2a will have 80% power to detect a difference in the proportion of patients with a 12-month e-PDC \geq 80% of 9.9% (e.g., 50.0% in control patients vs. 59.9% in intervention patients). For pre-post analyses of A1C outcomes, assuming α =0.05, SD=1.7, 1:1 intervention/control, and p=0.5 (correlation of repeated measures), and N=832, we expect 80% power to detect a clinically meaningful difference in A1C of 0.3% (e.g., 9.7% in control patients vs. 9.4% in intervention patients).

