H1.3 (Statin use): From preliminary data we estimate that 3,388 patients will meet study eligibility criteria due to having a statin-specific e-PDC <80%. Adjusting this estimate by half we anticipate N=1,694. Assuming a two-sided α =0.05, 1:1 intervention/control, and a probability of outcome (adherence) of 50%, the analysis for H1.3 will have 80% power to detect a difference in the proportion of patients with a 12-month e-PDC ≥80% for statin medications of 6.9% (e.g., 50.0% in control patients vs. 56.9% in intervention patients).

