9.3 POPULATIONS FOR ANALYSES

The **analysis population** is limited to subjects who meet intervention eligibility requirements at an index visit. We will use data from the Wizard algorithm runs outside the encounter at 6 and 12 months post-index visit to analyze the impact of the intervention on adherence (e-PDC) and clinical outcomes (A1C, BP, statin use). The cost analysis is limited to the subset of these patients who have HealthPartners insurance for at least 11 of 12 months after the index visit.

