9.4.2 ANALYSIS OF THE PRIMARY EFFICACY ENDPOINT(S)

Definitions of Dependent Variables (Aim 1): The primary dependent variables are described in Table 3 below.

Table 2. Description of Dependent Variables Used in Primary and Secondary Analysis.						
Variable	Description	Data Source	Classification			
PDC provided in	For each condition, achievement of e-PDC ≥80%	EMR	Binary			
the EMR (H1.1a,	for all medication classes for that particular					
H1.2a, H1.3)	condition (diabetes, hypertension, statin					
	indication) in the 12 months following index date.					
BP reduction Mean change in SBP from the last BP within the EMR vitals Contir		Continuous				
(mmHg) (H1.1b) 12 months prior to the index visit, to the last BP						
	value within 12 months after the index visit.					
Change in A1C Change in A1C value from the last lab test within EMR Continue		Continuous				
value (H1.2b) the 12 months prior to the index visit, to the last procedure						
	lab test within 12 months after the index visit.	results				

Drug-specific PDCs are extracted from Epic EMR. Key secondary dependent variables (also defined in Table 3) include (a) total 10-year ACC/AHA CV risk, and (b) other objective measures of medications adherence such as PDC calculated using claims data, and (c) survey assessed patient self-reported adherence using a validated instrument.¹¹⁰ We will assess additional dependent variables through a patient survey including barriers to adherence,¹¹¹ shared decision making,¹¹² health care satisfaction,¹¹³ and provider and pharmacist knowledge, attitudes, beliefs, and satisfaction with the CDS. **Analysis Plan for Aim 1 (Adherence and Outcome Hypotheses)**: Hypotheses H1.1a, H1.2a, H1.3 posit that patients assigned to the adherence intervention will be more likely than patients assigned to usual care to have high medication adherence (e-PDC ≥80%) in the 12 months following the index visit for BP medications (H1.1a), glucose medications (H1.2a), and statin medications (H1.3). Generalized linear model (GLM) regression with a logit link and binomial error distribution will be used to test the effect of the intervention. The general form of the analytic primary model for testing medication adherence is: $logit(Pr[PDC \ge 0.8]) = \beta_0 + \beta_1(Intervention) + \beta_c(Covariates)$

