The dependent variable in each model (antihypertensive medications, glucose-lowering medications, statins) is a binary indicator of high medication adherence (e-PDC \geq 80%) and is predicted by a binary indicator of adherence intervention assignment. We will screen and include patient characteristics in the model when they are unbalanced by treatment arm. In supplemental analyses, we will extend the GLM approach described above by including random intercepts to evaluate potential clustering effects at the level of clinic and/or provider.

H1 will be supported if the intervention group effect β_1 is significant and positive, supporting the prediction that clinical encounters with the adherence intervention are more effective than encounters without them for increasing medication adherence. Treatment group heterogeneity by patient sex, age group, race, insurance class, and comorbidity count will be assessed by including interaction terms consisting of products of patient variables and the intervention indicator.

Hypotheses H1.1b and H1.2b posit that patients assigned to the adherence intervention will be more likely than control patients to have reduced SBP (H1.1b) and reduced A1C (H1.2b) in the 12 months following the index visit.

 $E(Y)_t = \beta_{00} + \beta_{10}(Intervention) + \beta_{01}(Time) + \beta_{11}(Intervention * Time) + \beta_{c0}(Covariates)$ The analytic model will be a generalized linear model with an identity link and normal error distribution. The dependent variable Y (SBP for H1.1b and A1C for H1.2b) is predicted by a binary indicator of intervention assignment, time (pre-intervention vs. post), and the interaction of intervention assignment and time. We will screen and include patient characteristics in the model when

they are unbalanced by treatment arm, and will evaluate the potential for clustering by clinic and/or provider. A significant intervention group-by-time interaction term (P < 0.05) and a pre-specified contrast

A significant intervention group-by-time interaction term (*P*<0.05) and a pre-specified contrast indicating more reduction in SBP (H1.1b) or A1C (H1.2b) in the intervention than the control arm will support the prediction that encounters with the adherence intervention are more effective than encounters without it for improving BP and glycemic clinical outcomes.

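### Does leaving the e-PDC look-back length and source run unstated make the primary adherence outcome ambiguous?

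*Combined protocol and SAP*

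**What the plan says.** Table 2 in section 9.4.2 defines the binary outcome for H1.1a, H1.2a and H1.3 as an e-PDC of at least 80% for all medication classes of the condition over the 12 months after the index date. The analysis text repeats this as "to have high medication adherence (e-PDC ≥80%) in the 12 months following the index visit". The synopsis and sections 3 and 9.1 give the same 12-month period. Section 9.2 powers H1.1a on it ("80% power to detect a difference in the proportion of patients with 12month e-PDC ≥80% of 8.7% or more") and H1.3 likewise ("proportion of patients with a 12-month e-PDC ≥80% for statin medications").

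Three other places bear on how the value is obtained:

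- Section 9.4.2 says drug-specific PDCs are taken from the Epic record. Section 2.2 describes that score as calculated "for a specified measurement period of time (default time being 6 months) prior to a clinical encounter".
- Section 9.3 takes adherence and clinical outcomes from the "Wizard algorithm runs outside the encounter at 6 and 12 months post-index visit".
- The schedule of activities (1.3) says "Wizard algorithms are run outside of encounters on all study eligible patients at set intervals (6, 12, and 18 months) for analysis purposes".

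The decision rule in 9.4.2 rests on one coefficient per hypothesis: support is claimed if the intervention effect "is significant and positive, supporting the prediction that clinical encounters with the adherence intervention are more effective".

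**The concern.** The outcome is a score read from Epic, its look-back is a setting, and the only length given for that setting is 6 months. No sentence says it was changed to 12 months or that two 6-month scores are combined. Section 9.3 names two runs, while the logistic model has one outcome per patient and no time term. Two windows then seem possible: (A) a 12-month look-back at month 12, covering months 0-12, or (B) the default look-back at month 12, covering months 6-12.

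The 12-month phrase does not look decisive either. Section 9.1 uses it for blood pressure too ("a reduction in systolic BP in the 12-month period after the index visit"), and Table 2 then defines that outcome by a last value.

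The choice could matter because pharmacist outreach starts only after the 6-month re-evaluation (section 6.1.1). Window A includes about six months of decision support alone, and window B does not. If the setting were left open until results were known, the conclusion could depend on it and the 5% level would not hold.

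**Working it through.** **1. The plan's own figures.** Inputs from section 9.2: two-sided alpha 0.05, 80% power, 1:1 allocation, 50% adherent in the control arm. Per arm, with p̄ = (p1 + p2)/2 and d = p2 − p1:

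n = [1.96·√(2p̄(1−p̄)) + 0.842·√(p1(1−p1) + p2(1−p2))]² / d²

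Continuity-corrected: n_cc = (n/4)·[1 + √(1 + 4/(n·d))]²

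| Hypothesis | d | n per arm | n_cc per arm | Total with correction | Plan's N |
|---|---|---|---|---|---|
| H1.1a | 0.087 | 513.4 | 536.1 | 1,074 | 1,066 |
| H1.2a | 0.099 | 395.3 | 415.3 | 832 | 832 |
| H1.3 | 0.069 | 819.2 | 847.9 | 1,696 | 1,694 |

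The stated differences reproduce with the correction. The look-back does not enter the formula, so this neither supports nor excludes either window.

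**2. How the windows differ for one patient.** Assume a single drug, unchanged, and equal half-years with coverage x then y. Window A needs (x + y)/2 ≥ 80, so y ≥ 160 − x. Window B needs y ≥ 80.

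- 55% then 90%: (55 + 90)/2 = 72.5, so the patient fails A and passes B.
- 95% then 70%: (95 + 70)/2 = 82.5, so the patient passes A and fails B.
- Under A, x = 79 needs y = 81, x = 70 needs 90, x = 60 needs 100, and below 60 success is impossible.

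The documents do not give the share of patients in each range.

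**3. Error rate if the window were picked after seeing both results.** Under no effect, the two arm-comparison statistics are approximately bivariate normal, with correlation equal to that between the two binary outcomes. The rate is P(|Z1| > 1.96 or |Z2| > 1.96). The correlation is an assumption.

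| Correlation | False-positive rate |
|---|---|
| 0.4 | 9.3% |
| 0.6 | 8.8% |
| 0.8 | 7.8% |
| 0.9 | 7.0% |
| One window fixed in advance | 5% |

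**4. Whether the text leaves both windows open.** Every statement that defines or powers the outcome says 12 months. The 6-month figure occurs once as a measurement period, in a background account of the Epic product, and there as a default that can be changed.

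Table 2 also separates the outcome types. It asks for the last value within 12 months for systolic pressure and A1C, but sets no last-value rule for e-PDC. A proportion of days covered is a measure over a period, so a 12-month e-PDC most naturally names that period.

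**5. Which run.** A and B both read the month-12 run. A month-6 run cannot supply an outcome over the 12 months after index, and section 9.3 does not use the 18-month run. Section 6.1.1 gives the 6-month re-evaluation its own purpose: finding patients with persistent adherence problems for the outreach registry.

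**6. Other controls.** Section 10.1.9.1 says data collection is blind to assignment. It also promises operational definitions and technical specifications for elements that lack established ones, together with data dictionaries. A look-back set under those conditions does not inflate the error rate.

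**The case for a change.** The strongest case for a change is that the plan extracts a vendor score without giving its key setting, for three primary hypotheses, and that this can be fixed only before outcomes are seen. The size could be material. In an illustrative simulation the effect acts only in months 6-12, half-year coverage is beta-distributed with half the patients at or above 80%, and the halves correlate 0.3 to 0.7. An 8.7-point difference under B then becomes 4.6 to 5.2 points under A, and power at N = 1,066 falls from about 81-82% to 32-40%. Section 10.1.9.1 gives neither the look-back nor a date for fixing it. Success at either run is a further reading that the text does not rule out.

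Part of this stands. The look-back is not written down, and section 9.3 does not say how 6-month data enter the adherence models. The simulation, however, assumes no effect of decision support in the first six months, and a real early effect would shrink the gap. It compares two legitimate outcomes and does not show an error in the one the plan names. Measuring over months 0-12 is a defensible choice for a strategy that starts at the index visit. The either-run reading needs a combining rule that appears nowhere in the plan.

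**Conclusion.** The gap is real but narrow, and the plan can stand. The endpoint wording points to e-PDC over months 0-12, read at the month-12 run. What is missing is a statement that the Epic look-back was set to match, together with the analytic use of the 6-month run. The analysts would settle both when writing the extraction specification that section 10.1.9.1 already promises.

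Either window fixed in advance gives a valid comparison by assigned arm at 5%. The 7.0% to 9.3% range depends on a choice made after seeing results, which no part of the documents suggests, and on assumed correlations. It would apply to any two outcome definitions correlated to that degree. Adding a months 6-12 analysis would correct no wrong result, and the documents do not say whether a score for that window is stored. The conclusion rests on reading the repeated 12-month definition as governing over a background description of a product default.

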5 STUDY POPULATION

5.1 INCLUSION CRITERIA

To be eligible for the study, the patient must have an office visit with a clinician (physician or advanced practice provider) within a primary care department (family medicine, internal medicine, combined pediatric/internal medicine) at one of the 28 study clinics within the HealthPartners Medical Group or Park Nicollet care system, and meet all of the following criteria:

1. Age 18 to 75 years, inclusive. The evidence-based guidelines on which the CDS intervention is based are not applicable outside this age range.⁹¹

2. Have a primary care encounter (index visit) at a selected clinic.

3. Have a primary care encounter that meets one of or more of the following clinical criteria for care goals and medication adherence:

 In the 12 months prior to the index visit, most recent A1C ≥8% AND have one or more active non-insulin glycemic medications on their EMR medication list AND a potential adherence issue for one or more of these medications based on the Epic Medication Adherence score (e-PDC <80%, moderate or high confidence)

- Two consecutive encounters with BP values ≥140/90 mm Hg AND one or more BP medications on their EMR medication list AND a potential adherence issue identified (e-PDC <80%, moderate/high confidence)
- 3. Meet the ACC/AHA criteria listed below for moderate or high-intensity statin use AND a statin medication on their EMR medication list AND a potential statin adherence issue identified (e-PDC <80%, moderate/high confidence):
 - a. Age >21 with atherosclerotic CV disease identified by a CVD diagnosis on the problem list or two or more ICD-10 diagnostic codes in the last 2 years
 - b. Aged >21 and LDL >190 mg/dl
 - c. Aged 40 to 75 AND diabetes identified by the diagnosis on the problem list or two or more ICD-10 diagnostic codes in the last 2 years
 - d. Aged 40 to 75 with 10-year CV Risk Score 7.5% based on the ACC/AHA 10-year ASCVD risk equation.

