6.3 MEASURES TO MINIMIZE BIAS: RANDOMIZATION

Patients are randomly allocated 1:1 through a computer-generated program to either control or intervention. Contamination across intervention arms is unlikely because all patients receive CDS interventions based on their arm assignment. All patients assigned to the study arms are analyzed based on their arm assignment.

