10.1.9 DATA HANDLING AND RECORD KEEPING 10.1.9.1 DATA COLLECTION AND MANAGEMENT RESPONSIBILITIES

i. Data sources

All necessary data to determine eligibility, implement and operate the intervention, test the study hypotheses and assess the impact of the intervention are derived from (a) electronic health records EHRs, (b) health plan or medical group administrative databases, (c) feedback received directly from patients and providers by email or through the CDS feedback tab/links (d) surveys of samples of eligible patients in both study arms, (e) surveys of participating PCPs and pharmacists, and (f) interview transcripts and field notes

ii. Process steps for data acquisition

At each patient encounter in an intervention or control clinic, the CDS Web service will use EPIC generated medication adherence scores to identify potential adherence issues. Clinical decision support generated using the adherence data will be presented only at intervention clinics. At the index visit (the first visit in the 12-month enrollment period that study inclusion and exclusion criteria are met), the patient is assigned a unique study identifier that is used to link patient encounter data over time. All index and subsequent encounter data for eligible patients, including medications and adherence calculations, are securely stored behind a firewall within a limited de-identified analysis dataset. No effort is made to prevent or discourage control clinics from using their usual methods to assess and address medication adherence.

All data collection conducted is blinded to randomization assignment. We will establish common study variable definitions drawn from national standards, HEDIS Measurement Sets, and definitions used in previous studies.¹⁴¹ We will construct variable definitions and data extraction procedures for

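### The three primary adherence models do not prespecify index e-PDC as a covariate, although every patient has a qualifying value, so a modest, free gain in power is left to chance

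*Combined protocol and SAP*

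**What the plan says.** Section 9.4.2 fits H1.1a, H1.2a and H1.3 as logistic regressions. The 12-month indicator of e-PDC at or above 80% is the outcome "and is predicted by a binary indicator of adherence intervention assignment", and the formula also has a general covariate term. The main rule for filling that term is that patient characteristics are screened and included when unbalanced by arm. The section gives no test, threshold or variable list for this. Section 9.4 describes the patient characteristics taken from the EMR as demographics, payer and comorbid conditions. The missing-data paragraph of 9.4.2 adds a second conditional route: covariates that predict missing adherence outcomes may be included.

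The baseline value is available. Under section 5.1, the glycemic criterion requires "a potential adherence issue for one or more of these medications based on the Epic Medication Adherence score (e-PDC <80%, moderate or high confidence"), and the BP and statin criteria carry the same threshold and confidence requirement. Section 10.1.9.1 says "All index and subsequent encounter data for eligible patients, including medications and adherence calculations, are securely stored".

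Section 9.2 powers the adherence endpoints as simple two-proportion comparisons with no covariate adjustment.

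**The concern.** A patient entering at 75% coverage would ordinarily be expected to reach 80% more readily than one entering at 10%. If so, index e-PDC carries information about the outcome that the arm-only model leaves in the residual variation.

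Selecting covariates by observed imbalance does not address this. Under randomization a strong predictor will usually be balanced, and the rule would then leave it out. Adjusting for a prognostic baseline variable raises power even when it is balanced. The plan therefore leaves to chance whether the outcome's own baseline enters the primary model, and the model is not settled until the data have been seen. At stake is some efficiency in three primary tests, not their validity.

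**Working it through.** **1. Inputs from the documents.** Section 9.2: "Further assuming a two-sided α =0.05", 80% power, control adherence 50% in all three cohorts, and total N (difference) of 1,066 (8.7 points) for BP, 832 (9.9 points) for glycemic drugs and 1,694 (6.9 points) for statins. Section 6.3: "Patients are randomly allocated 1:1 through a computer-generated program". Table 1 in section 2.2: 45%, 50% and 36% of scored BP, diabetes and statin patients fell below 80%.

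**2. Reproducing the plan's figures.** Per arm, with pooled variance and d = p2 − p1,

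n = [1.960·√(2p̄q̄) + 0.842·√(p1q1 + p2q2)]² / d².

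For BP, p̄ = 0.5435:

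- n = [1.960·√0.4962 + 0.842·√0.4924]² / 0.087² ≈ 513.4, so 514 per arm and 1,028 in total.
- With the continuity correction, n' = (n/4)·[1 + √(1 + 4/(nd))]² ≈ 536.1, so 537 per arm and 1,074 in total.

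| Cohort | Stated N | N, continuity-corrected | N, uncorrected | Power at stated N, uncorrected |
|---|---|---|---|---|
| BP | 1,066 | 1,074 | 1,028 | 81.5% |
| Glycemic | 832 | 832 | 792 | 82.0% |
| Statin | 1,694 | 1,696 | 1,640 | 81.3% |

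The stated figures reproduce, and they do not rely on index e-PDC.

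**3. The missing input.** The documents give no relation between index e-PDC and 12-month success. The only repeated-measures correlation, 0.5, is for SBP and A1C. The strength is therefore assumed and varied.

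**4. Approximation.** If index e-PDC explains a fraction R² of the outcome variance, effective N is about N/(1 − R²). For BP at R² = 0.05, 1,066/0.95 = 1,122, or 56 extra patients; the same sum gives 44 (glycemic) and 89 (statin).

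| R² | BP | Glycemic | Statin |
|---|---|---|---|
| 0.02 | 82.2% | 82.7% | 82.1% |
| 0.05 | 83.4% | 83.9% | 83.2% |
| 0.10 | 85.3% | 85.8% | 85.2% |
| 0.15 | 87.2% | 87.7% | 87.1% |

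**5. Simulation allowing for the entry rule.** Latent normal adherence at index and 12 months with correlation r; patients restricted to the lowest 45%, 50% or 36% at index; control success 50%; 4,000 trials per setting (Monte Carlo error about 0.6 points). Power without → with index e-PDC:

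| r | BP | Glycemic | Statin | R² after restriction |
|---|---|---|---|---|
| 0 | 82.2 → 81.8% | 81.8 → 82.0% | 81.2 → 81.3% | 0 |
| 0.3 | 81.4 → 81.6% | 81.1 → 82.1% | 81.1 → 82.2% | about 0.02 |
| 0.5 | 81.6 → 83.5% | 80.7 → 83.7% | 81.2 → 83.3% | 0.054–0.067 |
| 0.7 | 81.7 → 87.2% | 81.2 → 87.9% | 79.9 → 86.9% | 0.13–0.16 |

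Restricting entry to values below 80% shrinks the gain: r = 0.5 leaves an R² of only about 0.05 to 0.07.

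**6. Does the imbalance screen recover the gain?** BP cohort, index e-PDC assumed uniform on 0–80%, screen taken as p < 0.05 (an assumption, since 9.4.2 gives no threshold). At log-odds 0.5 and 0.75 per SD, power is 83% and 82% never adjusted, 83% and 83% with the screen, and 84% and 86% always adjusted. The screen recovers little. Type I error with adjustment was 4.4–5.3%.

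**The case against.** **The model can adjust.** A reader might infer that index e-PDC is excluded. It is not: the formula has a covariate term, and there are two conditional routes into it. What stands is that neither route is a prespecification, and the main one recovers almost none of the gain.

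**No promised power is lost.** A reader might infer that the adherence tests are underpowered. Section 9.2 claims that "the analysis for H1.1a will have 80% power to detect a difference" of 8.7 points or more, and that claim holds unadjusted, as do those for the other two cohorts. This objection stands in full.

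**The gain may be small.** At 0.25 log-odds per SD, power is about 81% with or without adjustment. Gains to 88% or more at N = 1,066 can be simulated, but need about 1.0 log-odds per SD. With a uniform 0–80% distribution (SD 80/√12 = 23.1) and control success centred on 50%, the middle of the 0–10% band lies (40 − 5)/23.1 = 1.52 SD below the mean. That implies control success of about 18% there and 82% in the 70–80% band. Nothing in the documents supports so steep a gradient. Prediction may also be weakened by the endpoint, which covers all the condition's medication classes over 12 months, while entry needs one drug below 80% and the Epic score defaults to a 6-month window.

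**SBP and A1C are no precedent for a power gain.** Those models use the pre-value because the outcome is change. At the planned correlation of 0.5, the change-score SD for SBP is 15.8·√(2(1 − 0.5)) = 15.8, the same as for the post value alone.

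**Several drugs.** Only one qualifying value per cohort is assured, so BP and glycemic patients need a defined summary. This stands, and the fix must supply it.

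**Conclusion.** The point holds as a matter of efficiency and prespecification. Index e-PDC is assured for at least one qualifying drug per patient in each cohort and is stored, but none of the three primary adherence models names it in advance. Prespecifying it would be expected to add about 0 to 3 points of power for a latent correlation up to 0.5 and about 5.5 to 7 points at 0.7. If the relation is nil, the simulated differences (−0.4 to +0.2 points) lie within Monte Carlo error.

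These figures rest on an assumed correlation and distribution of index e-PDC. The direction is well supported, but the size is not fixed by the documents. They do not support a claim that the trial falls short of its stated power, that type I error is affected, or that index e-PDC is known to be the strongest predictor.

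**What to change.** In section 9.4.2, name continuous, condition-specific index e-PDC as a fixed covariate in the models for H1.1a, H1.2a and H1.3, whatever the observed balance. For patients on several drugs for a condition, state one summary in advance, for example the lowest moderate- or high-confidence value among that condition's drugs.

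Adding a covariate to a logistic model changes the arm odds ratio from marginal to conditional. Report the arm effect also as a standardized (marginal) risk difference, which is the scale used in 9.2.

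The number of condition drugs at index is an optional further covariate; its gain has not been shown.

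The cost is SAP wording and a short variable definition, with no new data collection and no change to sample size.
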